### Adverse Events

All operative and post-operative adverse events, whether voluntarily reported by the patient or observed by the investigator, will be recorded in the patient's study records.

### **3.4 Study Visits**

Each subject will attend 3 study visits. Each visit will have specified activities as described below.

#### Visit 1: Baseline (-1 to -90 days prior to surgery)

The baseline visit will occur to screen subjects, confirm study eligibility, complete the informed consent process, and enroll and randomize the subject.

- Informed consent
- Randomize patients meeting inclusion/exclusion criteria
- Collect demographics data, pre-operative knee history/diagnosis and employment status
- Visual Analog Scale (VAS) for knee pain
- Long standing AP and lateral x-rays to assess pre-operative mechanical axis alignment and posterior tibial slope. X-rays obtained within 6 months prior to surgery are acceptable for the baseline visit. The investigator may repeat x-rays if needed for clinical or imaging quality reasons.
- Complete CT scan or MRI for pre-operative planning and selection of cutting blocks (Group A Only)

#### Visits 2: Operative (Day 0-Discharge)

The following activities will be performed at each surgery visit.

- For all female patients of child bearing potential, pregnancy test will be administered prior to surgery as part of routine care by the hospital or surgery center.
- Surgery using instrumentation per randomization assignment
- Adverse event assessment
- Transfusion summary
- Bloodwork for hemoglobin assessment (measured at Day 1 or discharge if patient does not stay overnight)

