#### **Secondary Objectives:**

To compare the following surgical and clinical outcomes between the two study groups

- To compare correction of alignment after total knee replacement via long standing AP hip-knee-ankle x-rays.
- To compare the accuracy of tibial slope angle on a lateral knee x-ray
- To compare the number of trays sent to sterilization
- To compare the volume of estimated blood loss during the procedure
- To compare the drop in post-operative (day 1) hemoglobin and total volume of transfusions (allogeneic and/or autologous)
- To compare the occurrence of adverse events
- To compare the waste weight at the end of each surgery, considering separately those recyclable and those not recyclable.
- To compare the rate of intraoperative and post-operative complications
- To compare the rate of successful use of MyKnee® cutting blocks (i.e. the incidence of surgical cases where the surgeon did not need to abort the use of MyKnee intra-operatively and default to the use of standard cutting blocks).

The cost-per-minute value based on hospital estimates will be used to calculate an overall cost-savings total.

## 2

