### **STUDY DESIGN**

The study is a multi-center, prospective, randomized study comparing surgical and economic parameters of Total Knee Replacement performed with single-use Efficiency instruments with patient-specific technique (MyKnee®) versus traditional metal instruments with conventional surgical technique. The objective is to evaluate the impact of single-use instrumentation versus traditional metal instruments in reducing overall surgical costs and improving mechanical axis alignment. The timing of routine surgical phases will be measured, including the pre-operative preparation time, intra-operative phase, OR clean-up time and sterilization phase in 300 adult patients undergoing total knee replacement. AP and lateral x-rays will be utilized to assess the implant's mechanical axis alignment and tibial slope after discharge to the completion of the 6 week visit. Additionally, other parameters will be recorded including blood loss, post-op day 1 hemoglobin drop, adverse events, number of trays sent to sterilization, and total waste weight at the end of each procedure, considering separately those recyclable and those not recyclable. To ensure that the minimum of 300 patients is met, 342 patients will be randomized into two treatment cohorts in a 2:1 ratio.

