### Additional Operative Parameters

1. Estimated blood loss (cc)
2. Drop in post-operative hemoglobin (measured at Day 1 or discharge if patient does not stay overnight)
3. Total volume of transfusions (allogeneic and/or autologous)
4. Number of trays sent to sterilization
5. Waste weight at the end of each surgery; recyclable and non-recyclable (grams)

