#### Visit 3: 6 Weeks ( $\pm$ 3 weeks)

The following activities will be performed at the post-operative/discharge visit.

- Long standing AP x-ray to assess mechanical axis alignment
- Standard lateral x-ray to assess tibial slope
- Visual Analog Scale (VAS) for knee pain
- Adverse event assessment

Activity	Baseline	Operative	6 Weeks( ±3)
Informed Consent	X		
Baseline Details	X		
- Medical History	X		
- Eligibility Criteria	X		
- Demographics	X		
CT Scan or MRI for Pre-Operative Planning*	X*		
Randomization	X		
Visual Analog Scale (VAS) for knee pain	X		X
Pregnancy Test		X	
Operative Details		X	
- Timing for Pre-Operative Phase		X	
- Timing for Intra-Operative Phase		X	
- Timing for Sterilization Phase		X	
- Other Operative Parameters		X	
Adverse Events		X 	X 
Long Standing and Lateral Knee X-Rays	X		X

If applicable

\*Group A (Efficiency/MyKnee®) Only

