#### **4.1 Data Analysis**

The objectives of this study are outlined in Section 1.3. For purposes of this study, economic outcomes of interest include the peri-operative time, intra-operative time (OR efficiency), and sterilization times as quantitative values. These outcomes will be subsequently used in comparative cost analyses. The secondary objectives are to assess the accuracy of mechanical axis alignment and posterior tibial slope after total knee replacement, additional operative parameters, and adverse events.

Descriptive statistics, specifically means will be used to summarize the peri-operative, intra-operative and sterilization time data.

The primary objective will be met by comparing mean values of each of the time-saving parameters. The null hypotheses of no differences in mean values between re-usable and single-use devices will be tested using separate t-tests for two independent groups for each endpoint. A p-value of less than 0.05 will be considered significant for each endpoint. Endpoints with statistically significant differences are expected to contribute to expected cost differences to be determined in subsequent analyses.

Descriptive analyses as well as similar two-sample comparisons will be used to evaluate secondary measures.

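### The hemoglobin drop is a secondary endpoint, but the protocol schedules no pre-operative hemoglobin from which to compute it

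*Combined protocol and SAP*

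**What the plan says.** All references are to the combined protocol and SAP.

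- **Objective.** Section 1.3, Secondary Objectives: "To compare the drop in post-operative (day 1) hemoglobin and total volume of transfusions".
- **Design.** Section 2, Study Design: "other parameters will be recorded including blood loss, post-op day 1 hemoglobin drop".
- **Endpoint.** Section 3.3, Additional Operative Parameters: "Drop in post-operative hemoglobin (measured at Day 1 or discharge if patient does not stay overnight". Only the post-operative time is given.
- **Baseline visit.** Section 3.4, Visit 1 has "Collect demographics data, pre-operative knee history/diagnosis and employment status", plus consent, randomization, a pain score, x-rays and, for Group A, CT or MRI. It lists no blood test.
- **Operative visit.** Section 3.4, Visit 2: "Bloodwork for hemoglobin assessment (measured at Day 1 or discharge if patient does not stay overnight". This is the only hemoglobin sample scheduled anywhere.
- **Activity table.** It closes Section 3.4 and has no hemoglobin or laboratory row. The one row that could cover hemoglobin, "Other Operative Parameters", is marked at the operative visit only.
- **Analysis.** Section 4.1: "Descriptive analyses as well as similar two-sample comparisons will be used to evaluate secondary measures". It gives no starting value, look-back window, formula or covariate for the drop.

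**The concern.** A drop is a difference between two values, and the schedule supplies one. A site that follows Section 3.4 exactly collects no pre-operative hemoglobin. Section 3.5 has data reviewed against the protocol, so the gap need not raise a query. Whether it can be filled later depends on what each site happened to keep.

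Two outcomes are then likely. Either sites use chart values of differing age and source, or the analysis falls back on post-operative hemoglobin, which is not the endpoint the protocol states.

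Two smaller gaps affect the post-operative value. Sections 1.3 and 2 say day 1, while Section 3.3 and Visit 2 allow discharge for patients who do not stay overnight, so the sampling time varies. Transfusions are recorded, but not whether they came before the sample. A transfusion before the sample can mask part of the drop. The documents give no figure for the size of either effect.

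**Working it through.** **Step 1: is the missing baseline just this protocol's shorthand?** Compare how the plan treats other items.

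| Item | Baseline scheduled? | Reliance on routine care stated? |
|---|---|---|
| Alignment and slope x-rays | Yes: Visit 1 and activity table, with a 6-month look-back | Not needed |
| Pain score | Yes: Visit 1 and activity table | Not needed |
| Pregnancy test | Not applicable | Yes: Section 3.1.2 and Visit 2 |
| Pre-operative planning imaging | Yes, Group A: Visit 1 and activity table | Yes: Section 3.2 |
| Hemoglobin | No | No |

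Where the plan needs a pre-operative value it schedules one, and where it leans on routine care it says so. Hemoglobin has neither.

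**Step 2: what does the choice of analysis do to precision?** The plan states no precision or power figure for hemoglobin, so there is none to reproduce. Assumptions, none of them in the documents: equal pre- and post-operative SDs, correlation r between the two values, and complete data on all 342 patients. The arm sizes, 228 and 114, come from Section 4.2.

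Variance relative to a comparison of post-operative values alone:

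- post-operative only: 1
- simple drop: 2(1 − r)
- post-operative value adjusted for baseline: 1 − r²

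Smallest difference detectable with 80% power at two-sided 0.05, in SDs of a single hemoglobin value: (1.96 + 0.84) × √(1/114 + 1/228) × √(relative variance). The first two factors give 2.80 × 0.1147 = 0.32.

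| r | Drop: variance | Adjusted: variance | Post-only: detectable | Drop: detectable | Adjusted: detectable |
|---|---|---|---|---|---|
| 0.3 | 1.40 | 0.91 | 0.32 | 0.38 | 0.31 |
| 0.5 | 1.00 | 0.75 | 0.32 | 0.32 | 0.28 |
| 0.6 | 0.80 | 0.64 | 0.32 | 0.29 | 0.26 |
| 0.7 | 0.60 | 0.51 | 0.32 | 0.25 | 0.23 |
| 0.8 | 0.40 | 0.36 | 0.32 | 0.20 | 0.19 |

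**Step 3: reading the table.** At r = 0.5 the simple drop is no more precise than post-operative values alone, and below 0.5 it is less precise. The adjusted analysis is at least as precise as either at every r shown.

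**Step 4: do the three analyses target the same thing?** Under randomization the arms have the same expected pre-operative mean. The arm difference in mean drop is then the arm difference in mean post-operative value with the sign reversed. The adjusted model estimates that same difference, so it serves the stated objective.

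**The case against.** The strongest reply is that the drop itself is listed as something to be recorded, in Section 2 and again in Section 3.3. That would oblige sites to use a pre-operative value, presumably from the chart. The case report form is not among the documents, so what the data set holds is inferred. Section 3.5 draws data from source documents and has monitors ask sites to complete missing entries.

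This stands as far as it goes. A reader might infer that the endpoint cannot be computed at all, or that it will be missing for all 342 patients. The documents do not support that. They support only that the scheduled measurements are insufficient and that the share of patients affected is unknown. The chart reading does not remove the gap, because source, window and formula would still be undefined and could differ between sites.

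A reader might also infer that post-operative means would give a biased comparison. They would not, because treatment is randomized (Section 3.2.2). Nor does falling back on them always lose precision against the planned drop: at r = 0.5 the two are equal.

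Finally, estimated blood loss and transfusion volume are collected separately, so blood loss is still assessed in other ways.

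**Conclusion.** The point holds in this form: the hemoglobin drop cannot be computed from the measurements the protocol schedules, and nothing requires or defines the pre-operative value it depends on. The drop may be missing or inconsistently defined for an unknown share of patients.

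The precision at stake depends on an assumed correlation. From r = 0.5 to 0.8 with equal SDs, a simple drop has 1.00 to 0.40 of the post-only variance and the adjusted analysis 0.75 to 0.36. Adjustment improves the stated two-sample comparison; it does not correct a bias.

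This is one of several secondary endpoints. The primary time endpoints and the sample size do not depend on it. It should be repaired because prospective capture is cheap and later recovery is uncertain.

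**What to change.** 1. Add pre-operative hemoglobin (most recent routine value before incision, with its date) to the visit lists in Section 3.4, the activity table and the case report form.
2. Define the drop as the pre-operative minus the post-operative value.
3. Record the date and time of the post-operative sample and whether it preceded any transfusion. Reconcile the day 1 wording in Sections 1.3 and 2 with the discharge alternative in Section 3.3 and Visit 2.
4. In Section 4.1, replace the unadjusted two-sample test for this endpoint with a linear model of post-operative hemoglobin on arm, pre-operative hemoglobin and site. Site belongs in the model because randomization is done separately at each site.
5. Do not rely on a sensitivity analysis limited to day 1, pre-transfusion samples. Overnight stay and transfusion occur after randomization and may depend on arm or on bleeding, so that subset can be biased. Omit it or label it descriptive.

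**Cost.** One or two case report form fields, SAP wording and slightly more analysis work. No new test is needed where a routine count exists. Where none exists the value will be missing, and the SAP should say how those patients are handled.

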#### Visit 3: 6 Weeks ( $\pm$ 3 weeks)

The following activities will be performed at the post-operative/discharge visit.

- Long standing AP x-ray to assess mechanical axis alignment
- Standard lateral x-ray to assess tibial slope
- Visual Analog Scale (VAS) for knee pain
- Adverse event assessment

Activity	Baseline	Operative	6 Weeks( ±3)
Informed Consent	X		
Baseline Details	X		
- Medical History	X		
- Eligibility Criteria	X		
- Demographics	X		
CT Scan or MRI for Pre-Operative Planning*	X*		
Randomization	X		
Visual Analog Scale (VAS) for knee pain	X		X
Pregnancy Test		X	
Operative Details		X	
- Timing for Pre-Operative Phase		X	
- Timing for Intra-Operative Phase		X	
- Timing for Sterilization Phase		X	
- Other Operative Parameters		X	
Adverse Events		X 	X 
Long Standing and Lateral Knee X-Rays	X		X

If applicable

\*Group A (Efficiency/MyKnee®) Only

### 3.5 Case Report Forms

Case Report Forms (CRFs) are to be completed for all subjects.

All data is collected on study source documents and entered into the Case Report Forms by the Study Coordinator or delegated designee. All data will be reviewed for consistency and correctness with the protocol by the Investigator (or designee) and the Clinical Research Associate (CRA). All discrepancies requiring verification via an examination of the source documents will be sent to the study site for resolution or resolved during monitoring visits. During monitoring visits, the CRA will review all data, evaluate for completeness and have the site enter missing information and/or resolve errors. All entries, corrections and alterations are to be made by the responsible Investigator or his/her designee.

### 3.6 Study Documents

The following documents will be required by each site prior to activation:

- Signed protocol signature page
- Signed and dated written approval from the IRB of the protocol, informed consent form, and any applicable recruiting materials
- Signed investigator's agreement
- Financial disclosure form
- Signed and dated Delegation of Authority log
- Curriculum Vitae and medical licenses of applicable study staff

## 4

### STATISTICAL ANALYSIS PLAN

The Sponsor will evaluate for non-inferiority based on economic factors and the rate of adverse events between the two groups. The Sponsor may conduct additional post-hoc analyses of the study data after study completion. These analyses may be done for the purposes of publication or in conjunction with additional data that may be available to Sponsor from other sources.

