### **1.3 Study Objectives**

The objectives of this study are to compare economic factors and the rate of adverse events between two types of instrumentation used for total knee replacement:

- Single-use Efficiency Instruments with Patient Specific Technique (MyKnee®)
- Traditional Metal Instruments with Conventional Surgical Technique

The data obtained from this study could be useful for surgeons, facilities, and payors to help determine appropriate instrumentation in total knee arthroplasties.

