#### **4.2 Sample Size Analysis**

Sample size for this study was determined on the basis of device group differences observed in the Mont et al 2013 study for four (related) but important health care utilization endpoints. The table below summarizes the data in Table 2 of Mont et al, but also provides a summary of the comparisons between single-use and re-usable pooling over whether or not navigation was employed. These data were used to approximate the expected effect size (standardized mean difference) comparing between single-use vs re-useable instruments. The sample sizes required for a two sample t-test to obtain 80%, 85%, and 90% power as a function of the observed pooled effect sizes were determined. The effect sizes were derived from the reported mean differences and p-values. The maximum sample size per group required to achieve at least 80% statistical power to reject the null hypothesis of equal group mean was determined across the four outcomes summarized in Table 2. For the 2:1 allocation between the single-use Efficiency instruments with MyKnee versus traditional metal instruments, this sample size was 200:100 or total N=300. This value was increased by 14% to N=342 to account for uncertainty in the estimated effect sizes, to account and to allow for additional analyses of economic outcomes. Therefore, 228 and 114 patients will be randomly allocated into single-use Efficiency instruments and traditional metal instruments arms respectively.

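### The analysis plan announces a non-inferiority evaluation of economic factors and adverse events, but specifies only tests of no difference and gives no margin, bound or success rule

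*Combined protocol and SAP*

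**What the plan says.** The first sentence of the Statistical Analysis Plan (Section 4) reads "The Sponsor will evaluate for non-inferiority based on economic factors and the rate of adverse events between the two groups". Section 1.3 names the same two outcomes with a different aim: "The objectives of this study are to compare economic factors and the rate of adverse events between two types of instrumentation". Its secondary objectives include "To compare the occurrence of adverse events" and "To compare the rate of intraoperative and post-operative complications".

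Section 4.1 refers back to Section 1.3 and sets out the analysis. For the time parameters, "The null hypotheses of no differences in mean values between re-usable and single-use devices will be tested" by separate t-tests, each judged at p<0.05. For everything secondary, "Descriptive analyses as well as similar two-sample comparisons will be used to evaluate secondary measures". Cost comes later: of the time outcomes it says "These outcomes will be subsequently used in comparative cost analyses", without naming a test.

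Section 4.2 bases the sample size on "at least 80% statistical power to reject the null hypothesis of equal group mean" across four time outcomes. This gives 300 patients (200:100), raised by 14% to 342 (228:114). Section 2 treats 300 as the minimum to be met.

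**The concern.** A non-inferiority conclusion needs a margin fixed in advance and a confidence limit to compare with it. The plan has neither. Its only decision rule is p<0.05 for a difference, which answers another question: failing to reject equality does not show that an excess of some stated size has been ruled out.

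The gap affects both halves of the sentence, though unequally:

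- **Adverse events.** The trial is not sized for any adverse-event comparison and no expected rate is given. If the groups are truly alike, the likely result is a non-significant test, which the plan has no means of turning into a non-inferiority finding.
- **Economic factors.** A significant time saving settles the matter for that time endpoint. A non-significant time result does not. Nor does a significant time saving by itself show that cost is no worse, because the cost analysis is left for later.

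Section 1.3 expects the data to help surgeons, facilities and payors choose instruments, so a statement that one set is no worse on safety or cost could be acted on.

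**Working it through.** **1. The plan's own sample size.** Inputs from Section 4.2 and its table: set-up time, effect size 2.985/8.66 = 0.345, 80% power, 2:1 allocation. Alpha is 0.05 from Section 4.1; sidedness is not written.

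- Controls needed, two-sided: (1.960 + 0.842)² × (1 + 1/2) / 0.345² = 7.85 × 1.5 / 0.1190 = 98.9, so 99 and a total of 297. The noncentral-t calculation gives 300, as stated. A one-sided 0.05 test gives 234 and does not match.
- 300 × 1.14 = 342.

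The figure is therefore that of a two-sided difference test on a time endpoint. No margin and no adverse-event rate enters it.

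**2. Where the difference test does exclude inferiority.** If the 95% interval for the time saving lies wholly above zero, it also excludes any excess time with single-use instruments. At effect size 0.345 the power for this is 80.2% at 200:100 and 85.1% at 228:114.

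**3. Adverse events: what a non-significant result shows.** The rates here are assumptions. Section 4.1 names no test for proportions, so a pooled two-proportion z-test, two-sided 0.05, is assumed as well. Take 5% with metal (n=114) and 10% with single-use (n=228):

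- Pooled rate = (2 × 0.10 + 0.05)/3 = 0.0833.
- Standard error under equality = √[0.0833 × 0.9167 × (1/228 + 1/114)] = 0.0317.
- Standard error at the true rates = √(0.10 × 0.90/228 + 0.05 × 0.95/114) = 0.0285.
- Power = Φ[(0.05 − 1.960 × 0.0317)/0.0285] = Φ(−0.43) = 0.335.
- Chance of a non-significant result = 1 − 0.335 = 0.665. Exact enumeration of the same test gives 0.662; Fisher's test gives 0.69.

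If the true rates are equal, the chance is about 95% by construction. Non-significance is thus the more likely outcome in both situations. For a 5-point excess over other assumed control rates, at 228:114:

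| Control rate | 2% | 5% | 10% | 20% | 30% |
|---|---|---|---|---|---|
| Chance of p≥0.05 | 51% | 66% | 76% | 83% | 85% |

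**4. Adverse events: what margin the trial could support.** With equal true rates p and one-sided 0.025, the smallest margin with 80% power is (1.960 + 0.842) × √[p(1−p)(1/n₁ + 1/n₂)]. At p = 10% and 228:114 this is 2.802 × √(0.09 × 0.01316) = 2.802 × 0.0344 = 9.6 points.

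| Assumed rate | 5% | 10% | 20% | 30% |
|---|---|---|---|---|
| Margin at 342 | 7.0 | 9.6 | 12.9 | 14.7 |
| Margin at 300 | 7.5 | 10.3 | 13.7 | 15.7 |

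**5. One possible result.** With 37/228 (16.2%) against 11/114 (9.6%), the difference is 6.6 points and the pooled z-test gives p = 0.099. The Wald 95% interval is 6.6 ± 1.96 × 3.69, or −0.7 to +13.8 points. The result is not significant, yet it is compatible with an excess of nearly 14 points.

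**6. Cost.** No arithmetic applies: the documents give no cost figure, margin or test.

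**The case against.** The strongest reply is that non-inferiority is one stray term in an introductory line. The objectives, Section 4.1 and Section 4.2 all speak of comparing groups and testing for differences. Adverse events are one of nine listed secondary objectives, with no success criterion, and the descriptive analyses already planned leave room for a risk difference with an interval. Much of this stands, and it is why the remedy is small. It does not remove the contradiction: the sentence is a stated commitment, and Section 1.3 puts the adverse-event rate in the overall objective.

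A reader might infer that the sponsor intends to report a non-significant adverse-event p-value as proof of non-inferiority. The documents do not say so; they are silent on how such a result would be read. The point is that the plan offers no valid route to the announced conclusion.

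A second fair objection is that every event rate used here is assumed, and so is the test. That is right. The figures show scale only. That no result can be classed as non-inferior without a margin does not depend on them.

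**Conclusion.** The point holds as an inconsistency that should be corrected. Section 4 announces an evaluation of non-inferiority that Sections 4.1 and 4.2 cannot deliver. It affects adverse events, cost, and any time endpoint without a significant saving. On assumed rates, a doubling of adverse events from 5% to 10% would go undetected about two times in three at 228:114, and at a common rate of 10% only a margin of about 9.6 points would have 80% power.

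Two stronger readings are not supported. One is that the primary analysis or the sample size is undermined: the time tests, their alpha and the 300 and 342 figures stand as difference tests. The other is that 342 patients would suffice for an adverse-event non-inferiority claim while 300 would not. The documents give neither a rate nor a margin, so that line cannot be drawn from them.

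**What to change.** Replace the first sentence of Section 4 with: *Economic outcomes and adverse-event rates will be compared between the groups by the methods in Section 4.1.*

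Add at the end of Section 4.1: *For adverse events and for complications, the between-group difference in the proportion of patients affected will be given with its 95% confidence interval. A p-value above 0.05 will not be interpreted as non-inferiority or equivalence.*

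Keep the two-sample comparisons already planned, and add no new test of cost. Using the proportion of patients affected is a choice that gives the word rate a definite meaning.

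If the sponsor keeps a non-inferiority claim for adverse events or cost, it must fix and justify a margin for each before data are seen, decide from the relevant limit of the two-sided 95% confidence interval, and state the power at 342 and at the minimum of 300.

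The cost of the main fix is two edits and one added interval per safety endpoint. The sponsor gives up a claim that the plan cannot support. Keeping the claim costs more, because each margin needs justification and, depending on the margin and the true rate, the trial may be too small.
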